9.1.5 Administration of Investigational Medicinal Products

Intuvax

After thawing, all suspension in the vial, e.g. one (1) mL is drawn and the injection needle is filled. The vaccination is done into the viable part of the renal tumor using CT or Ultrasound guidance and monitoring for confirmation of administration location. There is no need to flush the needle with saline since the dead space in the needle has been accounted for.

The total volume injected is recorded on a worksheet and in the eCRF at each Vaccination Visit.

The Intuvax administration must be done by a trained and qualified radiologist/urologist/ /surgeon using an antiseptic procedure in a facility equipped for invasive treatment.

Sunitinib

Per oral administration initiated five (5) to eight (8) weeks after nephrectomy for all patients Administered dose should be in accordance with the SmPC/USPI.

In case of unacceptable sunitinib side-effects the standard on/off schedule of 4 weeks on/ 2 weeks off (schedule 4/2) can be changed to 2 weeks on/1 week off (schedule 2/1). Retrospective data from patients treated with schedule 2/1 (50 mg/day) indicates superior PFS compared to those obtained with schedule 4/2. In addition, the reported safety profile and tolerance for schedule 2/1 justify its use in place of schedule 4/2 [29].

9.2 Method of Assigning Patients to Treatment Groups

At Screening the patient will be assigned a site specific screening number. This number will be generated automatically by Trial-on-Line, the electronic data capture (EDC) system used in the study. The screening number will be in the following format XX-YYYY. The letter XX is the site number and YYYY the consecutive patient number starting at 1001 at each site. The screening number will be used to identify the patient throughout trial participation.

Two (2) randomization lists are generated by [REDACTED] using a global randomization system. One (1) to be used for randomization of high-risk patients and one (1) to be used for randomization of intermediate-risk patients. One (1) copy of each randomization list is kept in a sealed envelope in a locked cabinet at [REDACTED] and one (1) copy is sent to the IWRS provider. Randomization codes will be strictly sequential within blocks as patients are eligible for randomization. The randomization code will not be available to any person involved in the conduct or evaluation of the trial before the trial database is locked.

When all results from the assessments made at Screening are available and the Investigator has confirmed eligibility and Heng-risk category for the patient the study coordinator will log into the IWRS and receive randomization and treatment information. The study nurse will make a telephone contact with the patient and inform about treatment and timing of next study visit. *NB:* If local regulations and laws require a confirmatory diagnostic biopsy before vaccination (i.e. systemic treatment) patients randomized to Intuvax will be booked for a biopsy collection visit prior to Vacc1 Visit. All participating US patients need a diagnostic pre-biopsy made at Screening in order to evaluate eligibility for sunitinib treatment following nephrectomy.

In case a patient randomized to Intuvax and sunitinib treatment withdraws prior to first dose of Intuvax or a patient randomized to sunitinib treatment only withdraws prior to any assessments made at the first visit following Screening they are considered screening failures, *Section 8.5*. A patient withdrawal contact will be performed via the IWRS allowing for additional patient inclusion until 90 patients have initiated study treatment.

If a patient is not given treatment according to the randomization list, no attempt should be made to remedy the error once IMP has been dispensed. [REDACTED] must be notified as soon as the error is discovered and the error must be adequately documented.

9.3 Selection of Doses in the Study

Intuvax

The Intuvax dose to be administered in this study consists of 10×10^6 viable and HLA class II expressing DCs. The outcome of Immunicum AB's first-in-man study of Intuvax in RCC

patients (Protocol No.: IM-101 and EudraCT No.: 2011-002039-25) in which doses of 5×10^6 , 10×10^6 , and 20×10^6 DCs have been administered formed the basis for the dose selection.

The same dose of Intuvax will be injected two (2) times with a 14 ± 3 day interval into the viable part of the renal primary tumor during the period while the patient is awaiting nephrectomy. The patients will receive the vaccine cells from the same batch (i.e. the same donor) at both administrations. A survival of between 24 and 48 hours is expected for the injected DCs after the first vaccination and a considerably reduced survival after the second injection. On the other hand, the second administration triggers the inherent immune response memory initiated by the first administration. A 14 days period between dosing is suggested to avoid administration of a second dose to a patient with an exhausted immune system. This time-window also reflects the time between diagnosis and nephrectomy in routine care.

The suggested dose is also supported by the pre-clinical program on Intuvax that has been performed by Immunicum AB consisting of four (4) studies in rat. In order to mimic the human situation vaccine cells derived from circulating monocytes were used in the proof-of-concept study (VP10-14), the pilot-toxicology study (VP10-17), the toxicology study (VP10-43), and the biodistribution study (AB11-01). The toxicology study VP10-43 did not reveal any major changes in general health status, vital signs and laboratory parameters.

Sunitinib

The sunitinib dose to be administered in this study is in accordance with the SmPC/USPI from start of treatment.

Duration of treatment

Intuvax

Two (2) injections of Intuvax will be administered with 14 ± 3 days interval followed by Nephrectomy in accordance with local routine at least 3 days after the second vaccination and maximum 63 days from Screening.

Sunitinib

Administration to be initiated five (5) to eight (8) weeks after nephrectomy for all patients. Treatment will continue until End-of-Study (78 ± 2 weeks after Screening) unless terminated due to unacceptable side-effects or other reasons. For post study treatment see *Section 9.9*.

Active control, dosage and mode of administration

Sunitinib is the active control in this study, *Section 9.1.1*. Treatment (including dose adjustments etc.) will be in accordance with the SmPC/USPI from start of treatment.

9.4 Selection and Timing of Dose for Each Patient

The patients will be randomized to treatment when the results from all assessments made at Screening are available.

No time window between dosing of different patients applies in this study.

The time window between Intuvax doses for the individual patient is 14 ±3 days. If the individual patient experiences a DLT in connection with first vaccination, *Section 11.5* no second vaccination will be given to that patient.

9.5 Blinding

This is an open label study.

9.6 Prior and Concomitant Therapy

The following medications/therapies are prohibited during the study and within 28 days prior to Screening:

- Other investigational products
- Other systemic antitumor therapy.
- Local radiation therapy to any area except for the abdominal/retroperitoneal area including the kidney tumor is allowed. The impact of any palliative radiotherapy administered on evaluable lesions must be discussed with the Medical Monitor and documented in the eCRF

The following medications are prohibited within 7 days prior to Screening Visit until Nephrectomy:

- Systemic per oral corticosteroids exceeding 10 mg/day. However, inhaled, intranasal and local (per cutaneous) steroids for treatment of skin disorders, chronic obstructive lung disease, asthma, or allergy are acceptable irrespective of dose.

Specific instructions in relation to the nephrectomy and Intuvax vaccinations:

- Concomitant oral antithrombotic, e.g. acetylsalicylic acid (ASA), withdrawal and restart to be done according to local practice in connection with the nephrectomy and according to local practice for invasive examinations in connection with Intuvax vaccinations.
- Anticoagulants, local practice applies for start and stop of anticoagulant treatment and shift to/use of low molecular weight heparin treatment in connection with

nephrectomy and according to local practice for invasive examinations in connection with Intuvax vaccinations

Medication, which is considered necessary for the patient's safety and well-being, may be given at the discretion of the Investigator as per local guidelines and Standard of Care. Whenever there is a medication available to prevent or alleviate a symptom it will be offered to the patient.

Patients who respond inadequately to sunitinib treatment and need to change systemic anti-cancer therapy should be scheduled for an End-of-Study Visit before being withdrawn from the study, *Section 8.5*. As described in *Section 11.2* safety evaluation must also be performed up to 30 days after the patient's last dose of IMP administered in the study.

The use of all medication by the patient must be recorded in the eCRF, *Section 10.4.4*.

In connection with the surgery various concomitant medications such as anesthesia, fluid substitution/blood substitution are part of clinical routine and these concomitant medications should not be recorded in the eCRF. Only concomitant medications not normally used in connection with the post-operative course after nephrectomy should be recorded in the eCRF.

9.7 Treatment Compliance

Intuvax

Administration will be done at the clinic by trained study personnel. Treatment compliance will be accomplished by documenting in record (i.e. the drug accountability, preparation, administration logs, the patients' eCRF and medical records) information on, but not limited to: the batch number of the IMP used, the time-point for preparation/thawing, the time-point for administration, if CT or Ultrasound was used for confirmation of administration location, and signatures of designated site staff preparing and administering the IMP.

Any deviations will be documented on the appropriate eCRF page.

Sunitinib

Patient compliance will be evaluated by unused tablet counts and check of empty packaging. Patients will be asked to return all unused and empty packaging material at the next clinic visit. The number of unused tablets will be counted upon return and recorded in the drug accountability log kept at the site. The sunitinib compliance including any deviations will be documented in the patients' eCRF.

9.8 Drug Accountability

Intuvax and sunitinib accountability, i.e. documentation of deliveries and return between the manufacturer, storage center, pharmacy, and/or the clinic shall be maintained.

It is the responsibility of the Investigator or trained designee to determine Intuvax and sunitinib accountability and complete the drug accountability log.

Drug accountability will be reviewed by the monitor during interim site visits and at the completion of the trial.

At the end of the study when overall drug accountability have been completed any unused IMP should be handled by the pharmacy according to instructions provided by the Sponsor.

A list of IMP, used, or returned must be prepared and signed by the Investigator or designee; an account must be given for any discrepancies.

Copies of all Drug Receipt Confirmations, Returned Clinical Supplies Reconciliation Forms and Drug Accountability Logs will be retained in the study file. These forms are subject to regulatory inspection at any time.

9.9 Post Study Treatment

Intuvax is an IMP under development and will consequently not be available for treatment of the patients after study completion.

Immunicum AB will pay the patients' sunitinib treatment during their participation in the study except for US patients who have health insurance that covers these costs as part of standard of care.

After end of study participation, patients will continue treatment in accordance with clinical praxis, i.e. as per local guidelines and Standard of Care.

10 STUDY ASSESSMENTS

10.1 Primary, Secondary, [REDACTED] Endpoints

Primary endpoints

- OS from randomization overall in mRCC patients and by each subgroup, i.e. in high-risk and in intermediate-risk mRCC patients
- 18-month survival rate from randomization overall in mRCC patients and by each subgroup, i.e. in high-risk and in intermediate-risk mRCC patients

Secondary endpoints

- Frequency and proportion of AEs including clinical significant changes in laboratory tests and vital signs from Screening
- PFS from start of sunitinib according to RECIST 1.1*
- Proportion of Objective Response Rate (ORR) from start of sunitinib treatment and duration of response in each subgroup*
- TTP from start of sunitinib treatment*
- Relative number of tumor infiltrating CD8+ T-cells in the resected primary tumor compared to relative number of infiltrating CD8+ T-cells in available diagnostic pre-biopsy (sample from either primary tumor or metastasis acceptable)

*Note: For intermediate-risk patients included in the trial according to protocol versions before version Final 4.0, baseline for PFS, ORR and duration of response, and TTP is defined as the first imaging assessment after nephrectomy.

[REDACTED]

[REDACTED]	[REDACTED]
[REDACTED]	[REDACTED]
[REDACTED]	[REDACTED]
[REDACTED]	[REDACTED]
[REDACTED]	[REDACTED]
[REDACTED]	[REDACTED]
[REDACTED]	[REDACTED]
[REDACTED]	[REDACTED]

10.2 Efficacy Assessments

10.2.1 Primary Efficacy Variables and Assessments

10.2.1.1 Overall Survival (OS)

OS is defined as time from randomization to death from any cause.

The OS reported from patients according to Heng criteria in the two (2) different treatment arms is a primary efficacy variable.

10.2.1.2 Eighteen-(18)-Month Survival Rate

18-month survival rate is defined as the proportion of patients alive 18 months after randomization.

10.2.2 Secondary Efficacy Variables and Assessments

10.2.2.1 Progression Free Survival (PFS) from Start of Sunitinib

PFS from start of sunitinib is defined as time from Sunitinib Start Visit to PD or death following sunitinib initiation from any cause, whichever occurred first. PFS from start of sunitinib will be evaluated per stratum and in total from the two (2) different treatment arms as a secondary efficacy variable.

Note: For intermediate-risk patients included in the trial according to protocol versions before version Final 4.0, sunitinib treatment did not have to be initiated at a fixed time point. For these patients, the first imaging assessment after nephrectomy will be used as baseline for evaluation of PFS, irrespective of whether or not the imaging assessment coincided with sunitinib treatment start. Further details will be provided in the Statistical Analysis Plan (SAP).

10.2.2.2 Objective Response Rate and Duration of Response and Stable Disease from Start of Sunitinib

Evaluation of tumor response is based on centrally assessed CT scans, *Section 10.4.3*, according to the RECIST 1.1 guideline [1].

Definitions - RECIST v1.1

a) Measurable Disease

The presence of at least one (1) measurable lesion. If the measurable disease is restricted to a solitary lesion, its neoplastic nature should be confirmed by cytology/histology. The same measurable and non-measurable lesions will be followed by RECIST v1.1. Disease progression will be determined using RECIST v1.1 criteria.

- Malignant lymph nodes

To be considered pathologically enlarged and measurable, a lymph node must be >15 mm in short axis when assessed by CT scan (CT scan slice thickness

recommended to be no greater than 5 mm). At baseline and in follow-up, only the short axis will be measured and followed.

- **Baseline documentation of “Target” and “Non-Target” lesions**
All measurable lesions up to a maximum of 2 lesions per organ and 5 lesions in total, representative of all involved organs, should be identified as target lesions and recorded and measured at baseline.
 - **Target lesions.** Target lesions should be selected on the basis of their size (lesions with the longest diameter), be representative of all involved organs, but in addition should be those that lend themselves to reproducible repeated measurements. It may be the case that, on occasion, the largest lesion does not lend itself to reproducible measurement in which circumstance the next largest lesion which can be measured reproducibly should be selected. A sum of the diameters (longest for non-nodal lesions, short axis for nodal lesions) for all target lesions will be calculated and reported as the baseline sum diameters. If lymph nodes are to be included in the sum, then only the short axis is added into the sum. The baseline sum diameters will be used as reference to further characterize any objective tumor regression in the measurable dimension of the disease.
 - **Non-target lesions.** All other lesions (or sites of disease) including any measurable lesions over and above the 5 target lesions should be identified as **non-target lesions** and should also be recorded at baseline. Measurements of these lesions are not required, but the presence, absence, or in rare cases unequivocal progression of each should be noted throughout follow-up.

b) Response Criteria

Table 4 Target Lesions Evaluation Criteria

Complete Response (CR)	Disappearance of all target lesions. Any pathological lymph nodes (whether target or non-target) must have reduction in short axis to <10 mm.
Partial Response (PR)	At least a 30% decrease in the sum of the diameters of target lesions, taking as reference the baseline sum diameters
Progressive Disease (PD)	At least a 20% increase in the sum of the diameters of target lesions, taking as reference the smallest sum on study (this includes the baseline sum if that is the smallest on study). In addition to the relative increase of 20%, the sum must also demonstrate an absolute increase of at least 5 mm. (NB : the appearance of one or more new lesions is also considered progression).
Stable Disease (SD)	Neither sufficient shrinkage to qualify for PR nor sufficient increase to qualify for PD, taking as reference the smallest sum diameters while on study

Table 5 Non-Target Lesions Evaluation Criteria

Complete Response (CR)	Disappearance of all non-target lesions and normalization of tumor marker level
Progressive Disease (PD)	Appearance of one or more new lesions and/or unequivocal progression of existing non-target lesions ^a

Incomplete Response/ Stable Disease (SD)	Persistence of one or more non-target lesion(s) or/and maintenance of tumor marker level above the normal limits
------------------------------------------	------------------------------------------------------------------------------------------------------------------

^a Although a clear progression of “non-target” lesions only is exceptional, the opinion of the treating physician should prevail in such circumstances, and the progression status should be confirmed at a later time by the Investigator.

Evaluation of Best Overall Response

The best overall response is the best response recorded from the start of the treatment Sunitinib until disease progression/recurrence (taking as reference for PD the smallest measurements recorded since the treatment started). In general, the subject's best response assignment will depend on the achievement of the measurement criteria.

Table 6 Evaluation of Best Overall Response

Target Lesions	Non-Target Lesions	New Lesion	Overall response
CR	CR	No	CR
CR	Incomplete response/SD	No	PR
PR	Non-PD	No	PR
SD	Non-PD	No	SD
PD	Any	Yes or No	PD
Any	PD	Yes or No	PD
Any	Any	Yes	PD

Subjects with a global deterioration of health status requiring discontinuation of treatment without objective evidence of disease progression at that time should be classified as having “symptomatic deterioration.” Every effort should be made to document the objective progression even after discontinuation of treatment.

Note: For intermediate-risk patients included in the trial according to protocol versions before version Final 4.0, the first imaging assessment after nephrectomy will be used as baseline for evaluation of best overall response, irrespective of whether or not the imaging assessment coincided with sunitinib treatment start. Further details will be provided in the SAP.

Definitions for Response Evaluation

a) Confirmation of Response

To be assigned a status of complete or partial response, changes in tumor measurements do not need to be confirmed by repeat assessments after the criteria for response are first met.

b) Response rate

To be evaluated as the highest observed score of response during the study after randomisation in the ordinal categories of CR, PR, PD, SD and “Not evaluable”. The response rate will be evaluated according to the Schedule of Study Events, *Section 7.2.1*.

c) Objective response

Is defined as the proportion of patients with CR and PR.

d) Disease control rate (DCR)

Also called Clinical Benefit Rate is defined as the proportion of subjects with CR or PR or Stable Disease (SD).

e) The duration of response and stable disease

The duration of response is calculated for only those patients who responded. It was the time from first objective response to first observed progression of disease or death if the death was due to disease progression (whichever comes first).

The duration of stable disease is calculated for only those patients who exhibited a best response of stable disease response as per RECIST v1.1. It is the time from first SD response to first observed progression of disease or death if the death was due to disease progression (whichever comes first).

The duration of response and stable disease will also be calculated for the patients who responded and/or had a best response of SD.

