7.2.1.6 SFU[6W], SFU[12W], SFU[24W], SFU[36W], SFU[48W], and SFU[60W]

These visits are applicable for all patients unless locally CT-verified PD occurs. In case of PD this visit should be considered the End-of-Study Visit.

If SFU[60W] is scheduled ≥ 76 weeks since Screening this visit should be considered the End-of-Study Visit, *Section 7.2.1.7*.

TIME WINDOWS:

SFU[6W]: 6 weeks (± 7 days) after Sun-Start Visit
SFU[12W]: 12 weeks (± 7 days) after Sun-Start Visit
SFU[24W]: 24 weeks (± 7 days) after Sun-Start Visit
SFU[36W]: 36 weeks (± 7 days) after Sun-Start Visit
SFU[48W]: 48 weeks (± 7 days) after Sun-Start Visit
SFU[60W]: 60 weeks (± 7 days) after Sun-Start Visit

NB: The CT/MRI scans do not have to be done the very same day as the corresponding study visits. However, each CT/MRI scan has to be done within the specified time window for the corresponding visit.

ACTIVITIES AND ASSESSMENTS:

The same activities and assessments will be done at these visits as was done on Sun-Start Visit except for auto- and alloimmunization, *Section 7.2.1.5*. In addition to dispense of sunitinib, the site personnel will collect unused and empty sunitinib packages (distributed at the previous visit) from the patient for drug accountability, *Section 9.1.4*.

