10.2.2.3 Time to Progression (TTP) from Start of Sunitinib

TTP defined as time from Sunitinib Start Visit to date of first observed progression or date of death if the death was due to disease progression (whichever came first). Progressive disease is defined by RECIST v1.1 criteria and by clinical evaluation.

Note: For intermediate-risk patients included in the trial according to protocol versions before version Final 4.0, the first imaging assessment after nephrectomy will be used as baseline for evaluation of TTP, irrespective of whether or not the imaging assessment coincided with sunitinib treatment start. Further details will be provided in the SAP.

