10.4.3 Efficacy Assessments by Imaging

The locally assessed CT scan in conjunction with screening is to verify patient eligibility. This scan will be performed within 3 weeks before the Screening Visit unless a CT scan has been done in clinical routine within 6 weeks prior to the Screening Visit.

Brain imaging: every subject must have had a MRI of the brain during the screening period unless a brain imaging by (preferably by contrast enhanced) MRI or CT was performed within the 6 weeks before randomization date. The MRI brain may be replaced by a CT brain if the subject does not tolerate the MRI procedure.

On study, MRI (preferably contrast-enhanced) of the brain (or contrast-enhanced CT if not possible otherwise) should only be performed on the indication of evocative neurological symptoms.

Tumor response will be evaluated by means of CT preferably, contrast enhanced of the chest, the upper and lower abdomen (including pelvis) and all other suspected sites of disease. The tumor response will be evaluated according to RECIST v1.1. [1] at baseline and for all repeated measurements according to the Schedule of Study Events, *Section 7.2.1*.

CT scan assessments will be done both by a local radiologist trained in the study protocol and by a central assessor at the designated imaging CRO, [REDACTED], without knowledge of the patients' treatment assignment and Heng-risk profile. Central assessments will form the basis for endpoint evaluations (PFS, ORR, TTP, TTF and tumor response rate). Central assessments will be done in accordance with a separate study-specific imaging protocol provided by [REDACTED].

A study specific instruction describing the handling, transferring, blinding, distribution, assessment, result processing, and filing of data will be handed out to all involved personnel.

CT scans performed at Sun-Start Visit five (5) to eight (8) weeks after nephrectomy will be used for evaluation of PFS from start of sunitinib, *Section 10.2.2.1*. Note: For intermediate-risk patients included in the trial according to protocol versions before version Final 4.0, the first imaging assessment (i.e. CT scan) after nephrectomy will be used.

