6.3.6 Secondary Efficacy Analyses

PFS from start of sunitinib according to RECIST 1.1

PFS from start of sunitinib treatment will be derived as date whichever occurred first of any cause of death or date for first tumor progression (which is date for centrally assessed CT performed, according to RECIST 1.1) minus date for start of sunitinib treatment plus 1 day.

For the analysis of PFS only deaths occurring before end-of-trial will be accounted for in the analysis.

Analysis of PFS will be evaluated the following way:

Survival functions will be displayed graphically using Kaplan-Meier plots, and life table statistics will be produced including summaries of number of events and censored observations. Estimates of cumulative 25%, 50% (median) and 75% percentiles of survival with corresponding 95% confidence intervals will be calculated.

Comparison between Intuvax+sunitinib, vs. sunitinib alone will be done using a stratified log-rank test (controlling for strata intermediate/high risk), separate analyses will also be done by strata.

With protocol versions before version 4.0, intermediate risk patients did not have to initiate treatment with sunitinib at a fixed time point according to the visit schedule. Consequently some patients were never started on sunitinib, and in some cases sunitinib treatment was initiated at a later time point. The sunitinib start date constitutes the baseline time point for PFS according to protocol version 4.0 and after. In the analyses, patients who either had a delay or never started sunitinib will be included under the assumption that sunitinib treatment would have been initiated according to the final design, the date of the visit following the nephrectomy visit will be used as baseline.

Another issue that will be considered in the analysis is that some patients may have been discontinued based on general clinical disease progression as evaluated by investigator from symptoms/signs of disease, rather than based on a PD according to RECIST 1.1. For the analysis such cases will be handled strictly based on the RECIST 1.1 evaluation, thus if a patient is withdrawn without a CT confirmed PD the subject will be censored at last CT

Analyses will be based on FAS and repeated for separately by strata..

Proportion of Objective Response Rate (ORR) and Disease Control Rate (DCR) from start of sunitinib

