Response rate from Screening to Post-Nephrectomy

The evaluation of RECIST response rate between Screening and Post-Nephrectomy assessment will be summarised in the same way as described for response rate after Sunitinib Start Visit.

Time to tumor progression (TTP)

TTP from start of Sunitinib treatment will be derived as date for tumor progression, or clinical disease progression (other than RECIST 1.1) if occurring before tumor progression, minus date for start of sunitinib treatment plus 1 in the same way as done for PFS but excluding any deaths, if death before tumor or disease progression the subject will be censored at time of last CT during the trial. This variable will be analysed using the same method as for the evaluation of PFS.

Infiltrating CD8+ T-cells

The individual evaluation of intratumoral infiltration of CD8+ T-cells will be conducted as described in the protocol, where each patient will have the number of CD8+ T-cells/mm² counted from 3 areas in two separate biopsies by [REDACTED]. Each patients median of the 6 individual counts will be calculated. The patient median number of CD8+ T-cells will be summarised by treatment group, strata and overall using descriptive statistics for continuous data as described in Section 12.1.4.

At the GLP compliant laboratory [REDACTED] a validated automated quantification of intratumoral CD8+ T cells, using whole slide scanning instruments, will be performed. The tumoral area will be delineated by a trained operator and the surface of CD8+ labeling percentage will be assessed in the delineated areas. Each patients mean percentage from the two (2) primary tumor biopsies will be used for statistical evaluations. Patient's mean percentage will be evaluated for the treatment arms per stratum and in total using summary statistics, as described for continuous data in Section 6.3.2.

Relative number of tumor infiltrating CD8+ T-cells in the resected primary tumor compared to number of infiltrating CD8+ T-cells in available diagnostic pre-biopsy (sample from either primary tumor or metastasis), not be evaluated as described in the protocol due to missing pre-biopsy samples.

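### TTP counts clinical progression called by the unblinded investigator, although the protocol bases TTP on the blinded central read and SAP PFS censors the same patient

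*Protocol*

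**What the plan says.** The trial is open label (Protocol 9.5). Protocol 10.4.3 provides for a local and a central read of each scan. The central assessor does not know the arm or the risk group, and "Central assessments will form the basis for endpoint evaluations (PFS, ORR, TTP, TTF and tumor response rate". Protocol 10.2.2.2 repeats the principle for response: "Evaluation of tumor response is based on centrally assessed CT scans".

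The TTP definition departs from this. Protocol 10.2.2.3 states that "Progressive disease is defined by RECIST v1.1 criteria and by clinical evaluation". SAP 6.3.6 carries it into the derivation: the TTP date is tumor progression, "or clinical disease progression (other than RECIST 1.1) if occurring before tumor progression". The PFS part of SAP 6.3.6 describes clinical progression as an investigator judgement from signs and symptoms. TTP excludes deaths; a patient who dies before progression is censored at the last CT.

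For PFS, SAP 6.3.6 dates progression by the centrally assessed CT, treats clinical-only cases strictly by RECIST 1.1, and adds that "if a patient is withdrawn without a CT confirmed PD the subject will be censored at last CT".

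Protocol 10.2.2.2, Table 5 footnote a, says of progression confined to non-target lesions that "the opinion of the treating physician should prevail in such circumstances", and that "the progression status should be confirmed at a later time by the Investigator". It gives the central reader no role. The SAP does not mention this footnote.

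**The concern.** Clinical progression without RECIST progression is among the most subjective progression calls. Here it is made by someone who knows whether the patient was vaccinated. If investigators are slower to call it in vaccinated patients, or quicker in controls, TTP differs between arms with no difference in tumor growth. TTP has its own log-rank test and Kaplan-Meier figure in the SAP's table list, so the shift would be reported as a result.

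There is also a problem of coherence. SAP 6.3.6 says TTP is derived as PFS is, with deaths left out. On that description every TTP event would also be a PFS event on the same date, and TTP could not come out shorter. Adding clinical progression to TTP alone breaks this, so the two endpoints no longer use one definition of progression and cannot be read together.

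**Working it through.** The plan states no figure on this point and has no power calculation, so there is nothing to reproduce. The check has two parts.

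**1. The SAP rules applied to single patients.** Scans are due 6, 12, 24, 36, 48 and 60 weeks after sunitinib start. In each case the scans at weeks 6 and 12 show no progression.

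| What happens at week 16 | TTP | PFS |
|---|---|---|
| Withdrawn for clinical progression, no further CT | event, week 16 | censored, week 12 |
| Same, with a CT at week 16 showing no RECIST progression | event, week 16 | censored, week 16 |
| Dies without progression | censored, week 12 | event, week 16 |

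The first two rows show the split, which does not depend on a missing scan. The third row works the other way and lengthens TTP relative to PFS. The net direction depends on how often each case occurs.

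**2. Illustrative simulation of both rules.** From the documents: about 90 patients randomized 2:1, so 90 × 2/3 = 60 and 90 × 1/3 = 30; the scan times above; a two-sided 0.05 test. Assumptions not in the documents:
- exponential time to true RECIST progression, median m = 26, 43 or 52 weeks;
- death without progression at 0.004 per week;
- clinical calls in a share q of patients per 26 weeks, hazard −ln(1 − q)/26, independent of true progression, with withdrawal at the call;
- follow-up to week 60, no true arm difference, and an unstratified log-rank test (the SAP's is stratified).

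Medians in weeks, from 200,000 simulated patients per setting:

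| m | PFS, any q | TTP, q = 0 | q = 10% | q = 20% | q = 30% |
|---|---|---|---|---|---|
| 26 | 24 | 36 | 24 | 24 | 24 |
| 43 | 36 | 48 | 36 | 35 | 24 |
| 52 | 48 | 60 | 48 | 36 | 26.5 |

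Hand check for m = 43:
- TTP, q = 0: free of detected progression 0.5^(36/43) = 0.560 at week 36 and 0.5^(48/43) = 0.461 at week 48, so the median is 48.
- PFS: at week 36, 0.560 × exp(−0.004 × 36) = 0.560 × 0.866 = 0.485, so the median is 36.
- TTP, q = 30%: hazard −ln(0.7)/26 = 0.0137 per week. At week 24, 0.5^(24/43) × exp(−0.0137 × 24) = 0.679 × 0.720 = 0.489, so the median is 24.

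Arm-dependent calls, m = 43, 1,500 simulated trials per row. Hazard ratios are one-step (Peto) estimates, vaccine against control:

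| Calls per 26 weeks, vaccine vs control | TTP HR | TTP rejection | PFS HR | PFS rejection |
|---|---|---|---|---|
| 10% vs 10% | 1.00 | 5.3% | 1.00 | 5.1% |
| 10% vs 20% | 0.76 | 15.4% | 0.98 | 5.5% |
| 10% vs 30% | 0.59 | 40.4% | 0.97 | 4.9% |
| 5% vs 30% | 0.49 | 59.5% | 0.96 | 6.4% |

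The simulation error on a 5% rate is about √(0.05 × 0.95/1500) = 0.6 percentage points. With equal call rates TTP keeps its level, so the excess comes from the arm difference in calling. PFS under the SAP rule stays close to nominal. Because calls were independent of true progression, the simulation does not measure informative censoring of PFS after a clinical withdrawal.

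**The case against.** The strongest defence is that clinical progression in TTP is a declared protocol definition and not a slip in the SAP. Protocol 10.4.3 concerns imaging, so it can be read as choosing central over local scans for the imaging component only. On that reading PFS gives the strict RECIST view and TTP the broader one, and no rule in either document requires one to contain the other. Part of this stands: the definition is deliberate, so changing it must be declared. But 10.4.3 names TTP without exception, nothing reconciles it with 10.2.2.3, and the SAP itself describes TTP as PFS without deaths. Protocol 10.2.2.2 also puts deterioration without objective progression in a class of its own.

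Three stronger readings are tempting, and the documents do not support them.
- A reader might infer from footnote a that the treating physician decides PFS and best response. The SAP dates PFS by the central CT, Protocol 10.2.2.2 bases response on central CT, and the SAP never applies the footnote. It can be read as governing the local call, although it does not say so.
- Since "In case of PD this visit should be considered the End-of-Study Visit", a reader might infer that a clinical or non-target call rarely has a scan behind it. The End-of-Study Visit itself includes a CT (Protocol 7.2.1.7), is to be attempted for withdrawn patients (8.5), and is scheduled before a change of systemic therapy (9.6).
- A reader might put a number on the events affected. The documents give no rate for clinical-only progression, and they describe clear non-target-only progression as exceptional.

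All testing is exploratory and unadjusted. That lowers the stakes but does not remove bias from the estimate.

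**Conclusion.** The point holds for TTP. Protocol and SAP agree on counting an unblinded clinical call, against Protocol 10.4.3, and the SAP handles the same patient differently for PFS. It follows from the definitions alone that a patient can have a TTP event while censored for PFS. Whether TTP ends up shorter or longer than PFS is open, because deaths are censored in TTP.

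The size is unknown. The simulated hazard ratios of 0.76 to 0.49 and rejection rates of 15.4% to 59.5% show what unequal calling could do. They rest on assumed call rates and are not predictions for this trial.

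PFS and response are not directly affected under the SAP. PFS keeps one indirect exposure: censoring at the last CT after a clinical withdrawal may be informative. Footnote a is a protocol text that needs reconciling with 10.4.3 and the opening of 10.2.2.2. The primary endpoints, OS and 18-month survival, are untouched. This is worth correcting before database lock, at the level of a secondary endpoint.

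**What to change.** In SAP 6.3.6, derive the main TTP analysis from the same central RECIST 1.1 progression date as PFS. List this in SAP 6.1 as a change from Protocol 10.2.2.3, with the justification that Protocol 12.3 requires. The same entry can cover a related mismatch: Protocol 10.2.2.3 counts death due to progression as a TTP event, whereas the SAP excludes all deaths.

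Report TTP including investigator-assessed clinical progression as a labelled sensitivity analysis, with the number of such events per arm.

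State that Table 5 footnote a applies to the local assessment only, and that the central reader's non-target assessment decides PFS, TTP and ORR. These changes concern endpoint derivation and leave patient management as it is.

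The cost is a declared change, some wording and one extra run. The main TTP analysis will have slightly fewer events. Patients withdrawn for clinical progression will be censored in it, possibly informatively, which the sensitivity analysis addresses.
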